3.4 Outcomes

This trial will have two primary outcomes, one around essential components for ANC, and one for essential components for PNC.

Outcome 1 (ANC): Essential components included in the composite measure of integrated services specific to ANC visits are listed below.

- EC1 = Respectful maternity care indicators:
 - Introductions, greeting the woman, consent, questions
- EC2 = Screening for Pre-eclampsia:
 - Measure BP

- Test urine for proteinuria
- EC3 = Screening for, prevention and management of Anaemia:
 - Measure Haemoglobin
 - Provide ferrous sulphate with folic acid
- EC4 = Screening for, prevention and management of Malaria:
 - Checked for clinical symptoms and test for Malaria if relevant
 - Provide treatment if needed
 - Provide bed nets if not provided yet
 - Provide Intermittent Presumptive treatment
- EC5 = Screening for, prevention and management of HIV:
 - Test for HIV
 - Provide Prevention of mother to child transmission care (PMTCT)
 - Provide anti-retroviral drugs (ARV) for mother if needed
- EC6 = Screening for, prevention and management of Syphilis:
 - Test for syphilis
 - Provide antibiotics if needed
- EC7 = Screening for, prevention and management of Tuberculosis (TB):
 - Checked for clinical symptoms and test for TB
 - First line TB drugs or referral if needed
- EC8 = Prevention of Tetanus in mother:
 - Tetanus toxoid vaccination
- EC9 = Screening and counselling for mental health and domestic violence:
 - Screening tools
 - Counselling services
- EC10 = Estimation of BMI:
 - Assess maternal height
 - Assess maternal weight
- EC11 = Prevention of post- and pre-term birth:
 - Estimate gestational age
- EC12 = Assessment of foetal wellbeing during pregnancy, Screening for multiple pregnancy, abnormal lie and presentation during pregnancy:
 - Assess growth using fundal height measurement
 - Assess foetal heart rate (FHR)
 - Abdominal palpation
- EC13 = Provide advice on birth preparedness and danger signs of pregnancy:
 - Consultation

The outcome for each ANC visit will be a score which measures the proportion of the above components that was delivered during that visit (EC_ANC).

The score will measure the proportion of essential components delivered in full. All thirteen essential components listed above are applicable for ANC. Some essential components

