involve multiple components, at least one of which is always applicable; some components are only applicable to a subset of clients, eg HCP counsels the woman about mental health is only applicable if the client's response to a previous question is cause for concern. All essential components will carry a weight of 1. The overall score will be derived by aggregating the weighted scores for each essential component which will then be converted to a percentage. Six essential components are binary; hence the score can only be 0 (not achieved), or 1 (achieved and single weighted); in some cases the determination of this involves an algorithm. The other seven essential components are not binary as they have sub-components assessed independently and thus may be partially achieved and carry an intermediate score, eg a multiple of 0.25 for essential component 1 (respectful maternal care).

Outcome 2: Essential components included in the composite measure of integrated services specific to PNC visits are listed below.

- EC1b = Respectful maternity care indicators:
 - Introductions, greeting the woman, consent, questions
- EC2b = Screening for Pre-eclampsia:
 - Measure BP
- EC3b = Screening for, prevention and management of Anaemia:
 - Measure Haemoglobin
 - Provide ferrous sulphate with folic acid
- EC4b = Screening for, prevention and management of Malaria:
 - Checked for clinical symptoms and test for Malaria if relevant
 - Provide bed nets if not provided yet
- EC5b = Screening for, prevention and management of HIV:
 - Test for HIV
 - Provide Prevention of mother to child transmission care (PMTCT)
 - Provide anti-retroviral drugs (ARV) for mother and baby
- EC6b = Screening for, prevention and management of Syphilis:
 - Test for syphilis
 - Provide antibiotics if needed
- EC7b = Screening for, prevention and management of Tuberculosis (TB):
 - Checked for clinical symptoms and test for TB
 - First line TB drugs or referral if needed
- EC8b = Prevention of Tetanus in mother and baby:
 - Tetanus toxoid vaccination
- EC9b = Screening and counselling for mental health and domestic violence:
 - Screening tools
 - Counselling services
- EC10b = Provide advice and support regarding breastfeeding:
 - Consultation

- EC11b = Offer postpartum contraception:
 - Consultation
- EC12b = Monitor newborn growth:
 - Weigh the baby
- EC13b = Clinical examination of the mother:
 - Examine the mother
- EC14b = Clinical examination of the baby:
 - Examine the baby

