Observation of each HCP in multiple assessment periods will improve the power of the trial to detect an improvement in outcomes, since underlying differences between individual HCPs will be able to be modelled using random HCP effects. However, shift patterns will limit the availability of participating HCPs, so at some HCFs it may be necessary to conduct observations on two different dates within a step to be able to observe at least two HCPs in each assessment period. In facilities where both ANC and PNC clients are seen by each participating HCP observations for both primary outcomes will be able to be completed using the same HCPs. For other facilities, where ANC and PNC clinics are completed by different sets of staff on any given shift it may be preferable to recruit 4 to 6 HCPs, some to be observed providing ANC and others PNC. This would enable HCPs in both clinics to be observed on some observation days, thereby reducing the number of observation days in the assessment period. **Box 2** summarises the sample size planned.

Each interaction (ANC and PNC) observed will be assessed for the corresponding primary outcome.

The R shiny app ($\frac{\text{Hemming}}{\text{Memming}}$, 2019) was used in February 2020 to perform power calculations for this design, using a continuous response, with a standard deviation of σ . The standard deviation, σ , is the square root of the total variance, which aggregates the various components of variance. The app is not designed for the additional level of observation within HCP, so the data considered for purposes of sample size calculation is the mean across four observations for each HCP at the HCF.

Box 2: Sample size details

Number of clusters (HCFs):	18
Number of steps:	6 (8 assessment periods)
Duration of steps:	6-7 weeks
For each HCF:	
Number of HCPs per primary outcome*:	3 (or 2)
Number of periods in which care at HCF is assessed:	4
	(periods 1, 3, 5 and 7
	or 2, 4, 6 and 8)
Number of HCPs assessed for each primary outcome per assessment period:	At least 2
Number of HCP-client interactions assessed for each primary outcome per HCP assessed in an assessment period	4

^{*} where clinics combine ANC and PNC clients the same HCPs can be used for both; where ANC and PNC clinics are separate different sets of HCPs may be used.

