The residual variation (σ_{error}) is assumed not to exceed 0.2 for individual assessments, so the residual variation for means for assessment of 4 visits would not exceed 0.1. For the random effects we assume that each of σ_{HCF} , $\sigma_{HCP|HCF}$ and σ_{HCF^*month} does not exceed 0.15 in value. (A standard deviation for HCPs ($\sigma_{HCP|HCF}$) of 0.15 would occur if the means for HCPs in a given month have a range of about 0.6 and 65% of the means are within a range of 0.3, within a possible range of values of 1.0 (Figure 2 displays two such distributions). With these values the overall standard deviation would then not exceed 0.28 =sqrt(0.01+0.0225*3), when means of 4 observations for 3 HCPs per HCF are used and an improvement of 0.81*0.28=0.23 would be detectable with at least 80% power. For other scenarios the upper limits on the difference detectable is indicated in the table below. If all HCPs are assessed as assumed the absolute differences detectable with 80% power are likely to be smaller than indicated in the table, since the variances are unlikely to take values as large as assumed.

[figure not shown]

Figure 2: Examples of distributions with standard deviation of 0.15

However, it is expected that some HCFs will only have two HCPs able to participate in the trial, and that in some steps when assessment is planned some HCPs will not be assessed due to logistic reasons. These reductions in the volume and structure of data would increase the difference detectable. Sample size formulae are not available to adjust the sample size if some HCPs are not assessed on all planned occasions. To examine the likely impact of such shortfalls in the planned sample size two small simulations were performed to examine the impact on standard errors of the estimated intervention effect and thus of the difference detectable:

- i) A reduction in the number of HCPs available at half of the HCFs from 3 to 2;
- ii) Observation of only one (of 3) HCPs per HCF in each assessment period.

For each scenario a dataset was generated using the design details and an intervention effect of 0.1 (approximately 1 additional item addressed on average). Each dataset was analysed as planned. For each dataset ten subsets were then also derived and analysed as planned.

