3.8 Statistical analysis

Period is defined as the assessment period of the trial which observation occurred, or for which measurement took place. Data will be omitted from analysis when values are missing for either the outcome or a covariate required for the analysis of that data value. Missing data will not be replaced.

For each ANC/PNC visit observed the proportion of essential components addressed will be calculated (ECall). Data analysis will be performed using Stata version 14.2 or later. To derive an estimate of the benefit of providing ANC-PNC training, linear regression within a generalised linear mixed model (GLMM) framework will be used to analyse the primary outcome data (ECall). GLMMs are appropriate in the context of stepped wedge trial designs as they allow for clustering and address confounding of intervention effects and time (Hemming et al 2015). The analysis will include a binary intervention factor which indicates if the data were collected pre- or post- ANC-PNC training and fixed effects for study month to account for any underlying secular trend. Random effects will be included for HCF (cluster), HCP within HCF and HCF by month interaction. The effects of the intervention will be reported as an adjusted (for month, HCF and HCF by month clustering) odds ratios (OR), with 95% confidence intervals.

Reporting will follow CONSORT guidelines for reporting stepped wedge trials current at the time of publication of the results (currently Hemming et al, 2018), Available data will be analysed using an intention to treat approach and also as implemented, if there are any protocol deviations, to assess the sensitivity of results to the analysis approach adopted.

The baseline delivery of essential components has been assumed to be around 50% as the precision of estimates is poorest for this value. If the level is below 50% there will be greater potential for improvement and greater power to detect an improvement of a specified magnitude. However, if the level is close to 100% it will not be possible for a statistically significant benefit of the intervention to be demonstrated. In such circumstances administrative analyses will be conducted.

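### Section 3.8 fits a linear mixed model to the primary score but promises an odds ratio; the effect that model estimates is a difference in mean score

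*Protocol*

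**What the plan says.** Section 3.4 defines the ANC outcome for each visit as "a score which measures the proportion of the above components that was delivered during that visit (EC_ANC"), and derives the PNC outcome in the same way. Six of the thirteen ANC components are scored 0 or 1. The other seven "may be partially achieved and carry an intermediate score, eg a multiple of 0.25 for essential component 1". Appendix 2 gives sub-points of 0.2, 0.25, 0.4 and 0.5, and section 3.4 converts the total to a percentage.

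Section 3.6 used software "to perform power calculations for this design, using a continuous response, with a standard deviation of" σ, and states its detectable differences as absolute changes in the score.

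Section 3.8 says that "linear regression within a generalised linear mixed model (GLMM) framework will be used to analyse the primary outcome data (ECall"). The model has a before/after training indicator, fixed effects for study month, and random effects for HCF, HCP within HCF and HCF by month. The paragraph ends with the reporting rule, which also asks for a 95% interval: "The effects of the intervention will be reported as an adjusted (for month, HCF and HCF by month clustering) odds ratios (OR").

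**The concern.** The model and the effect measure stand in the same paragraph and do not fit together. In a linear regression the training coefficient is a difference in mean score, adjusted for time and clustering. An odds ratio needs a logit link, a binary outcome or a stated conversion, and the protocol gives none of these.

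The rule governs the headline result of both primary outcomes. If it stays, the reported effect either departs from the stated measure or comes from a model or conversion chosen later, possibly with the data in view. An odds ratio also could not be set directly against the detectable differences on which the trial was sized. The protocol itself fixes both the model and the measure, so this is not a detail left to a statistical analysis plan.

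**Working it through.** **1. The plan's own sizing figures (section 3.6 and Table 5).**

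- The stated upper limit on the standard deviation is: "the overall standard deviation would then not exceed 0.28 =sqrt(0.01+0.0225*3"). Check: √(0.01 + 0.0675) = √0.0775 = 0.278.
- Three HCPs, four visits each: 0.81 × 0.28 = 0.227, stated 0.23.
- One HCP, four visits: 0.95 × 0.278 = 0.264, stated 0.26.
- With one visit per HCP the standard deviation is √(0.04 + 0.0675) = 0.328, giving 0.81 × 0.328 = 0.266 (stated 0.27) and 0.95 × 0.328 = 0.311 (stated 0.31).

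All four reproduce, taking 0.81 and 0.95 from the protocol as given. They are differences in mean score. The simulated effect of 0.1 is on the same scale: 0.1 × 13 = 1.3 ANC components, in line with the protocol's own gloss of about one more item.

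**2. What an odds ratio could mean here.** The control mean is p0 = 0.50 (the baseline assumed in section 3.8), and the difference is d = 0.23 (detectable limit) or d = 0.10 (simulated effect). Two readings are possible:

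- Exponentiate the linear coefficient: exp(d).
- Take the ratio of odds of the two mean scores: [(p0 + d)/(1 − p0 − d)] ÷ [p0/(1 − p0)].

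For d = 0.23: exp(0.23) = 1.26; (0.73/0.27) ÷ (0.50/0.50) = 2.70.

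For d = 0.10: exp(0.10) = 1.11; (0.60/0.40) ÷ (0.50/0.50) = 1.50.

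The two readings disagree, and neither is the quantity that the linear model estimates. If the score is analysed as a percentage, the first reading becomes exp(23), about 9.7 × 10⁹, or exp(10), about 22,026. Neither is a usable effect measure.

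**3. Whether one coefficient fixes one odds ratio.** Only the 0.50 baseline is the protocol's. The others are assumptions.

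| Control mean | Ratio of odds, d = 0.23 | Ratio of odds, d = 0.10 |
|---|---|---|
| 0.30 (assumed) | 2.63 | 1.56 |
| 0.50 (protocol) | 2.70 | 1.50 |
| 0.60 (assumed) | 3.25 | 1.56 |
| 0.70 (assumed) | 5.69 | 1.71 |

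Example, last row: (0.93/0.07) ÷ (0.70/0.30) = 13.29 ÷ 2.33 = 5.69. The same linear effect gives different odds ratios at different baselines, so the coefficient alone does not supply one.

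**The case against.** The best defence is that a generalised linear mixed model can have a logit link, and that parts of section 3.8 suggest thinking on the proportion scale. The outcome is called a proportion, and a 50% baseline is chosen because precision is said to be worst there, which is how a binomial proportion behaves. A score between 0 and 1 with partial credit is not a binomial count, but a fractional-response logit model can be fitted to it and would give an odds ratio. That much stands, and it would be too strong to say that the score rules out a logit model. The protocol does not specify one, however. It says linear regression, and its sample size rests on a continuous response. Adopting a logit model would be a change to the primary analysis and would need its own power basis.

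A second defence is that a competent analyst would simply report the mean difference. That is likely. A reader might infer that analysts are forced either to exponentiate the coefficient or to switch to a logistic model. The documents do not support this, since the linear model already gives a usable estimate and interval. Reporting it would still depart from the measure laid down for both primary outcomes.

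A reader might also infer from the reporting sentence that HCP clustering has been left out, because its parenthesis lists only month, HCF and HCF by month. The sentence before it includes HCP within HCF as a random effect, so nothing is missing from the model.

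**Conclusion.** The effect measure in section 3.8 is wrong for the model specified there. What the plan estimates is a difference in mean score. At the 0.50 baseline, the detectable limit of 0.23 would appear as 1.26 or 2.70 depending on how an odds ratio was manufactured, and the simulated effect of 0.1 as 1.11 or 1.50. These figures use the protocol's baseline and differences. The values at 0.30, 0.60 and 0.70 rest on assumed baselines. The 0.23 is an upper limit on the detectable difference, not an expected effect.

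The error lies in the stated scale of the result. It does not bias the linear fit, alter the hypothesis test or change any sample size figure. With 18 clusters, a reader might go further and infer that the planned test has an inflated type I error. The protocol does not support that reading: it names neither the estimation method nor the reference distribution, and these are commonly left to the statistical analysis plan.

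**What to change.** In the reporting sentence of section 3.8, replace the odds ratio by the adjusted difference in mean score, in percentage points, with its 95% confidence interval, taken from the linear mixed model already specified. Leave that model as it stands: the training indicator, the fixed effects for study month, and the random effects for HCF, HCP within HCF and HCF by month.

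The cost is one sentence. Design, data collection and sample size figures do not change, and the result can be read directly against the detectable differences of 0.23 to 0.31. If the sponsor does want an odds ratio, the protocol would have to specify a logit-link model for a fractional response and redo the power basis on that scale, which is a larger change and is not needed to remove the contradiction.

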3.9 Quality assurance

3.9.1 Data collection and processing

Generally, data used in the trial will be managed with the overall technical oversight provided by the international team in CMNH-LSTM, responsible for the budget and workplan. Beyond logistics, the team will provide paper forms and/or electronic devices (tablets) with robustly designed and pre-tested tools (on Survey CTO as a platform) and will ensure that complete

and consistent data sets are collected and uploaded to LSTM secure servers. LSTM will train the two data collectors for observation, in partnership with the Ministry of Public Health and CSSI-CRASH.

Once the data collection team has been organised, a national central-level team from CSSI-CRASH, linked to the Ministry of Public Health and CMNH-LSTM, will oversee the day-to-day quality assurance. This joint team will oversee data uploading in N'Djamena and ensure quality assurance and report progress to LSTM and, if necessary, facilitate in-country communication for any issues encountered. All healthcare facilities will be informed of the contact details of their local 'data contact', who will be the go-to person for any queries relating to data issues.

The M&E officers in charge of observation and data collection will be responsible for uploading data correctly and on time (according to a pre-agreed schedule), and that all data is has been checked for accuracy before uploading from the tablets to the LSTM server. They will be responsible for escalating any issue to the local coordinator and further to LSTM to allow for timely inputs on problem-solving.

Platforms for data collection will (preferably) be electronic, where additional validations and checks can be in-built into the tools, further enhancing the quality of data collected. The logistics and training requirements of the different platforms for the study team will be agreed ahead of the data collection process. At present, plans for Chad are that electronic data collection is undertaken with back-up paper forms available in case of equipment malfunction.

Support mechanisms for ensuring quality of data collection will be devised with the support of CSSI-CRASH and where possible periodic visits to N'Djamena will be conducted to offer support, in addition to the ongoing remote support via mobile communication platforms.

Data transfer will be agreed and monitored in cooperation with the CMNH-LSTM team, who use trackers and QA systems on all studies to ensure checks and balances of data received but also cleaning of data contents.

Data cleaning will be undertaken by trained research assistants using Standard Operating Procedures developed specifically for the tools used in the field; the checks will include verification of missing data, outliers but also responses which otherwise can be classed as non-conformities. These will be managed by consulting where necessary with the teams on the ground for corrections which can be made by on-the-ground follow up, while management of those that cannot be verified will be discussed on a case-by-case basis with the senior statistician to minimise data loss or risk of introducing bias, while maintaining data quality. All changes will be noted, and both the original and final datasets preserved for audit purposes.

3.9.2 Data analysis

Data analysis will be conducted using quality assured scripting in Stata, which will be kept for any verifications. Data analysis will be conducted by a senior statistician at LSTM, with support and ongoing discussions with the team in Liverpool and on the ground to provide timely inputs for interpretation of the results.

3.9.3 Data storage and transportation

Data collected by healthcare facilities and utilised for their quality improvement activities, will be managed and stored locally according their agreed standards. Both individual devices and servers are password protected and data encrypted in transfer to minimise any risk of data exposure. For any paper records, secure location for their storage will be identified and systems for transport of the paperwork agreed to protect the data.

Data shared with LSTM for the trial, will be stored in line with standard LSTM data management and storage procedures. If used, paper forms will be scanned and stored electronically in limited access locations on LSTM servers, which are backed-up regularly. Following confirmed receipt, any paper forms will be disposed of in accordance with incountry regulation on safe disposal of records. Electronic data will be kept securely on LSTM servers, backed-up regularly. Once data work has been completed and forms uploaded, tablets will be cleared of any data, and working and final datasets will be stored on LSTM system, with access restricted to the core research team, under the guardianship of the M&E team. In-country partners will receive a copy of the final dataset as well as any other materials which are to be shared under the partner agreement. Any other data sharing will need to be agreed with the PI and conform to the data sharing policies. Following the completion of the trial, all data will be kept for a minimum of 5 years at LSTM.

An audit trail of data and any changes due to cleaning will be stored alongside the trial documentation.

